7. AEs, and therefore all serious adverse events (SAEs), and incidents will be recorded from immediately after signing the informed consent form (ICF) until 5 days after the last use of investigational toothpaste. Incidents will be recorded from first to last use of the medical device (the manual toothbrush used to apply the acclimatization and investigational toothpastes).

Property of Haleon- Confidential

May not be used, divulged, published or otherwise disclosed without the consent of Haleon

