5.6 Screen Failures

Screen failures are defined as subjects who consent to participate in the clinical study but are not subsequently randomized. To ensure transparent reporting of screen failure subjects, a minimal set of screen failure information will include demography, screen failure reason (e.g., withdrawal of consent), eligibility criteria, any protocol deviations and any AEs, as applicable.

Individuals who do not meet the criteria for participation in this study (screen failure) will not be re-screened.

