12.2 Populations for Analysis

12.2.1 Definitions of Analysis Populations

The Safety population will comprise all randomized subjects who receive at least one dose of investigational product. Summaries and analyses of this population will be based on the investigational product the subject received.

The primary population for the assessment of efficacy will be a modified intention-to-treat (mITT) population. The mITT population will comprise all randomized subjects who receive at least one dose of investigational product and complete at least one-post Baseline DH efficacy assessment. This population will be based on the investigational product the subject was randomized to. All subjects who receive a randomization number will be considered randomized.

The Per-Protocol (PP) population will comprise all subjects in the mITT population who have at least one DH efficacy assessment considered to be unaffected by protocol deviations.

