12.3.4 Safety Analyses

Safety analyses will be performed on the Safety population, according to investigational product received. AEs will be regarded as 'treatment emergent' if they occur on or after the first use of investigational product at Baseline (Visit 2). In the event of a missing start date, an AE will be assumed to be 'treatment emergent' unless the end date is prior to starting treatment. In case of misallocation, compared to the randomization schedule, TEAEs will be associated with the most recent study investigational received.

Each AE will be categorized as oral or non-oral by the investigator or medically qualified designee. All will be reviewed by the CRS and coded using the MedDRA prior to database lock and unblinding.

A listing of all AEs will be presented for all subjects in the Safety population with the following AE summaries (number of distinct AEs and frequency/proportion of subjects affected) presented by treatment group and overall:

- TEAEs
- TEAEs by System Organ Class (SOC) and Preferred Term (PT)
- TEAEs by Oral/Non-Oral and PT
- Treatment emergent treatment related AEs by Oral/Non-Oral and PT
- Treatment emergent treatment related serious AEs by SOC and PT

Separate listings will be presented for:

- Deaths, SAEs and any AEs leading to product or study discontinuation.
- OST findings (with a summary of abnormalities by visit)
- OHT findings (with a summary of changes by visit)
- Exposure to study product ([Section 12.3.6.1.](#))

Medical device incidents will be listed; if there are no incidents, a null listing will be produced. While no specific risks or anticipated adverse device effects are expected from use of the medical device (manual toothbrush) provided, any medical device incidents reported during the conduct of this study will be assessed to evaluate the safety of the device.

Property of Haleon- Confidential

May not be used, divulged, published or otherwise disclosed without the consent of Haleon

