4.1 Populations for Analysis

4.1.1 Subject Disposition

Screen failures are defined as subjects who consent to participate in the clinical study but are not subsequently randomized. An enrolled subject is a subject who has signed informed consent and is eligible to proceed beyond the screening visit.

The number of subjects screened, enrolled, and randomized subjects will be presented in Table 14.1.1.

The number and percentage of screen failure subjects (subjects not randomized) with reasons why subjects are not randomized will be displayed. Percentages for screen failure subjects will be based on the total number of subjects screened.

The number and percentage of randomized subjects who complete and discontinue the study, broken down by reason for discontinuation, by study product and overall will also be displayed. The percentages will be based on the number of subjects randomized.

Table 14.1.1 will also present the number and percentage of subjects in each of the defined analysis populations (as defined in [Section 4.1.3](#)) by study product and overall. Percentages will be based on the number of subjects randomized.

Subject disposition including demographic data (age, sex, race and ethnicity), screening date, study product start date and time, subject status (completer, Yes/No), study completion /withdrawal date, duration (in days) in the study (defined as [(date of completion or withdrawal – start date of study product) + 1], and the primary reason for withdrawal will be listed (Listing 16.2.1.1) by study product.

Subject disposition information will be listed for non-randomized subjects (Listing 16.2.1.2), displaying subject number, demographic information (age, sex, race, and ethnicity), screening date, reason for screen failure and any further details of reason for screen.

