4.1.3 Analysis Populations

Three analysis populations are defined.

Population	Definition / Criteria	Analyses Evaluated
Safety	Comprise of all randomized subjects who receives at least one dose of study product. Any subject who receives a randomization number will be considered to have been randomized. This population will be based on the treatment the subject actually received.	
• Safety
Modified Intent-To-Treat (mITT)	Comprise all randomized subjects who complete at least one dose of study product and have at least one post-baseline DH efficacy assessment.	
• Demographic• Baseline Characteristics• Efficacy Analysis

Population	Definition / Criteria	Analyses Evaluated
	
Any subject who receives a randomization number will be considered to have been randomized.
 
This population will be based on the study product to which the subject was randomized.
	
Per-Protocol	
Comprise all subjects in the mITT population who have at least one DH efficacy assessment considered to be unaffected by protocol deviations.
 
Protocol deviations that would exclude subjects from the PP population are defined in Section 4.1.2 (Protocol Deviations).
 
This population will be based on the study product to which the subject was randomized.
	
Efficacy Analysis

NOTES :

Please refer to [Appendix 1: List of Data Displays](#) which details the population to be used for each displays being generated.

The numbers of subjects included in each of the analysis populations will be summarized (Table 14.1.1). Subjects excluded from any of the analysis populations will be listed in Listing 16.2.3.1, with the reason for exclusion.

The primary population for assessment of efficacy will be the mITT Population. A PP analysis will be performed on the DH endpoints. If at least 10% of the mITT subjects are excluded from the PP Population, a decision on whether a PP analysis will be performed will be made prior to study unblinding (release of the randomization codes).

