4.5.1 Adverse Events and Serious Adverse Events

All AEs will be reviewed by the Clinical Research Scientist or Designee prior to database lock and will be coded to a system organ class (SOC) and preferred term (PT) using the Medical Dictionary for Regulatory Activities (MedDRA).

AEs will be classified as oral and non-oral on the AE page of eCRF.

Treatment emergent adverse events (TEAEs) are defined as new AEs that occur on or after the first study product use (if this date is missing a suitable alternative will be used e.g., date of randomization). AEs with an onset date/time prior to the first study product use will be considered as non-treatment emergent.

The following summary tables and listings will be presented by study product.

-
- Table of TEAEs by SOC and PT (Table 14.3.1.1).
 - Table of TEAEs by Oral/Non-Oral and PT (Table 14.3.1.2)
 - Table of treatment related TEAEs by SOC and PT (Table 14.3.1.3)
 - Table of treatment related TEAEs by Oral/Non-Oral and PT (Table 14.3.1.4)
 - Listing of all AEs (Listing 16.2.7.1 for safety population)
 - Listing of deaths (Listing 14.3.2.1)
 - Listing of non-fatal SAEs (Listing 14.3.2.2)
 - Listing of TEAEs leading to study or drug discontinuation (Listing 14.3.2.3)
 - Listing of TEAEs classified as Oral (Listing 14.3.2.4)

In the event that there is nothing to report, a null table or listing will be produced.

All incidents will be listed in Listing 16.2.7.2. In the event that there is nothing to report, a null listing will be produced.

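### No planned table or listing shows adverse events, deaths or device incidents in subjects who used the acclimatization toothpaste and study toothbrush but were not randomized

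*SAP*

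**What the plan says.** **Collection starts before randomization.** Protocol 10.3 collects AEs and SAEs from signature of consent. The AE definition in Protocol 10.1 expressly covers the acclimatization product and the device. For the toothbrush, footnote 7 to Protocol Table 1-1 states: "Incidents will be recorded from first to last use of the medical device". First use is the supervised brushing at Screening (Protocol 8.1.7.1).

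**Reporting is tied to randomization.** Protocol 12.2.1 says "The Safety population will comprise all randomized subjects who receive at least one dose of investigational product". SAP 4.1.3 has the same restriction: "Comprise of all randomized subjects who receives at least one dose of study product". SAP 4.5.1 plans a "Listing of all AEs (Listing 16.2.7.1 for safety population". Appendix 1 gives the same population to the listings of deaths (14.3.2.1), non-fatal SAEs (14.3.2.2), TEAEs leading to discontinuation (14.3.2.3), oral TEAEs (14.3.2.4) and incidents (16.2.7.2).

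**Non-randomized subjects have one listing.** SAP 4.1.1: "Subject disposition information will be listed for non-randomized subjects (Listing 16.2.1.2), displaying subject number, demographic information". The remaining fields are the screening date, the reason for screen failure and further details of that reason.

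**Protocol 5.6** sets a minimum of information for screen failures, defined as subjects who consent but are not randomized. That minimum includes "any protocol deviations and any AEs, as applicable".

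**The concern.** The collection window and the reporting population do not match. A subject can pass Screening, use two sponsor-supplied products for two to four weeks, have an adverse event or a toothbrush incident, and then not be randomized. The event is in the database, but no planned output is built to display it.

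Two things are at stake. First, SAP 4.5.1 calls for a null listing when there is nothing to report. Followed literally, the plan could print a null listing of deaths, SAEs or incidents although one had occurred during acclimatization in a subject who was never randomized.

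Second, the omission can be selective. Some subjects will leave because of what happened during acclimatization. For example, antibiotic use in the two weeks before Baseline is an exclusion (Protocol 5.3, criterion 12), and the illness behind it may be an AE. Acclimatization events are listed for subjects who go on to be randomized and dosed, but not for those who do not.

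**Working it through.** The main check is a comparison of passages; the plan states no figure on this point to reproduce.

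**Step 1. Match each display to its population (SAP 4.5.1 and Appendix 1).**

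| Display | Content | Population |
|---|---|---|
| Tables 14.3.1.1 to 14.3.1.4 | TEAEs and treatment-related TEAEs | Safety |
| Listing 14.3.2.1 | Deaths | Safety |
| Listing 14.3.2.2 | Non-fatal SAEs | Safety |
| Listing 14.3.2.3 | TEAEs leading to discontinuation | Safety |
| Listing 14.3.2.4 | Oral TEAEs | Safety |
| Listing 16.2.7.1 | All AEs | Safety |
| Listing 16.2.7.2 | Incidents | Safety |
| Listing 16.2.1.2 | Disposition, no AE or incident field | Non-randomized |

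All six event listings are on the Safety population. The default in SAP section 4, all randomized subjects, would not reach this group either.

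**Step 2. Compare with the governing text.**
- Protocol 5.6 includes AEs in screen-failure information; Listing 16.2.1.2 has no field for them.
- SAP 4.5.1 says without qualification that every incident goes into Listing 16.2.7.2. The restriction comes only from the population column of Appendix 1.
- For the all-AE listing, the SAP follows the protocol. Protocol 12.3.4 reads: "A listing of all AEs will be presented for all subjects in the Safety population". That restriction therefore starts in the protocol.
- Protocol 12.3.4 lists any AE leading to product or study discontinuation. SAP Listing 14.3.2.3 narrows this to TEAEs, while SAP section 5 declares no change from the protocol.

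**Step 3. Size, under a stated assumption.** The documents do not give the number enrolled but not randomized. Assume 10% to 40% of enrolled subjects are not randomized.
- Enrolled = 234 / (1 − f). At 10%: 234 / 0.90 = 260, so 26 not randomized. At 40%: 234 / 0.60 = 390, so 156 not randomized.
- Unlisted toothbrush days: 26 × 14 = 364 at the low end; 156 × 28 = 4,368 at the high end.
- Listed toothbrush days are the randomized subjects' treatment days plus their own acclimatization days, because Listing 16.2.7.1 covers all AEs and not only TEAEs. Treatment: 234 × 56 = 13,104. Acclimatization: 234 × 14 = 3,276 or 234 × 28 = 6,552. Totals: 16,380 or 19,656.
- Unlisted share: 364 / (16,380 + 364) = 364 / 16,744 = 2.2%; 4,368 / (19,656 + 4,368) = 4,368 / 24,024 = 18.2%.

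The calculation gives each subject full acclimatization use and each randomized subject the full 56 days. Subjects who leave early would have fewer days.

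**The case against.** A reader might infer that these events are never reported. The documents do not support that. All AEs from consent are recorded in the eCRF, SAEs go to the sponsor within 24 hours (Protocol 10.3 and 10.4.2), and so do device incidents (Protocol 10.10.2). Onward regulatory duties are set out in Protocol 10.8 and 10.10.4. Appendix 1 also has a heading for narratives of deaths and serious events (14.3.3) with no population stated, so a narrative is neither planned nor excluded. A serious event would not go unseen. This stands, and it confines the point to the planned displays.

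A reader might also infer that an AE causing withdrawal before Baseline leaves no trace. It could appear as the reason for non-randomization in Table 14.1.1, or in the reason and details fields of Listing 16.2.1.2. That stands too, but a disposition reason does not identify an AE or SAE as such, and it does not capture events that were not the reason for leaving.

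A third tempting reading is that the SAP contradicts Protocol 12.3.4. For the all-AE listing it does not. The protocol's sentence that "any medical device incidents reported during the conduct of this study will be assessed to evaluate the safety of the device" promises assessment, not a listing of all consented subjects, and the section opens by placing safety analyses on the Safety population.

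Protocol 5.6 can be read as a data-collection rule, met by the eCRF. It does not name a listing. Its stated aim, though, is transparent reporting of these subjects, so a listing that leaves out their AEs falls short of it.

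Finally, the unlisted exposure is to a commercial fluoride toothpaste and a commercial toothbrush with no specific risks anticipated (Protocol 2.2), and the safety objective concerns the investigational toothpastes. That supports a low severity.

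**Conclusion.** The point holds as a minor gap in reporting completeness. No planned table or listing presents AEs, SAEs, deaths or device incidents for consented subjects who used the acclimatization toothpaste and toothbrush but were not randomized. This falls short of Protocol 5.6 and of the SAP's own statement on incidents. Both documents need the change, because the limit on the all-AE listing begins in Protocol 12.3.4. The TEAE wording of Listing 14.3.2.3 is a related, separate departure from the protocol and does not raise the severity.

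The finding itself rests on the text and needs no assumed rate. Only its size does: 26 to 156 subjects and about 2% to 18% of toothbrush exposure if 10% to 40% of enrolled subjects are not randomized. Some such subjects are to be expected, since teeth must qualify again at Baseline (Protocol 8.2.1.5). Setting the 4,368 high-end days against the 13,104 treatment days alone would suggest 33%, but that ignores the acclimatization days of randomized subjects, whose events are listed. No efficacy estimate, p-value or between-arm safety comparison is affected.

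**What to change.** - In SAP 4.5.1 and Appendix 1, set Listings 14.3.2.1, 14.3.2.2, 16.2.7.1 and 16.2.7.2 to all consented subjects, with non-randomized subjects in a separate 'Not randomized' group.
- Amend Protocol 12.3.4 so that its listing of all AEs, and its listings of deaths, SAEs and incidents, name the same population.
- Restore Listing 14.3.2.3 to any AE leading to product or study discontinuation, as Protocol 12.3.4 already states.
- Leave the by-arm TEAE tables on the Safety population.

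The cost is a change of population label on four listings, one event criterion, a matching protocol edit and slightly longer listings. No new data are needed, because the events are already collected in the eCRF.

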4.5.2 Other Safety Variables

Other safety variables are listed below:

- OST examination
- OHT examination

4.5.2.1 OST Examination

This procedure will be conducted by a qualified, experienced clinical examiner. The OST examination will be accomplished by direct visual observation and palpation, using retraction aids as appropriate, and will include examination of the labial mucosa (including lips), buccal mucosa, mucogingival folds, gingival mucosa, hard palate, soft palate, tonsillar area, pharyngeal area, tongue, sublingual area, submandibular area and salivary glands. The results of the examination will be recorded in the eCRF as either 'normal' or 'abnormal'; details of any abnormalities will be documented in the eCRF.

Any observation that changes from 'normal' to 'abnormal', or worsens, from the OST examination completed at Screening will be recorded as an AE.

OST will be summarized (number of subjects and percentages with abnormalities, without abnormalities, or OST not examined) by visit and study product in Table 14.3.4.1 for all subjects in Safety Population. OST examination will be listed (Listing 16.2.8.1) for Safety Population.

4.5.2.2 OHT Examination

This procedure should be conducted by a qualified, experienced clinical examiner. The OHT examination will be accomplished by direct visual observation, using retraction aids as appropriate, and will identify enamel irregularities, tooth fractures, grossly carious lesions/gross decay, defective/faulty restorations (both direct and indirect restorations, including fixed/

removable prostheses), non-carious tooth surface loss (abrasion, attrition, abfraction and erosion), any other hard tissue irregularities (e.g., hypo- and hypermineralization, decalcification) and significant tooth staining. Observations will be listed as 'absent' or 'present'; conditions noted as 'present' will be described in the eCRF.

Any observation that changes from 'absent' to 'present' or worsens from the OHT examination completed at Screening will be recorded as an AE. The presence of any implants, fixed or removable dentures, fixed or removable orthodontic braces/bands, fixed orthodontic retainers, full crowns or veneers will be recorded, along with evidence of gross intra-oral neglect or the need for extensive dental therapy.

OHT examination will be listed (Listing 16.2.8.2) for safety population.

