2.1 Background and Rationale for Study

CSPS (tradename NovaMin®) was originally developed as a bone regenerative technology due to its ability to bond with bone tissue ([Hench, 1971](#); [Hench, 1973](#); [Hench, 1980](#)). It was first marketed in a fluoridated, daily use toothpaste (5% w/w CSPS) by GlaxoSmithKline (now Haleon) for the relief of DH in 2011 and continues to be sold globally (more than 60 countries), primarily as *Sensodyne Repair & Protect*. CSPS is included in the investigational toothpaste at 5% w/w to provide relief from the pain and discomfort of DH.

Randomized controlled trials (RCTs) with 4-12 weeks (typically 8 weeks) treatment duration (e.g., [Acharya, 2013](#); [Du, 2008](#); [Gendreau, 2011](#); [Hall, 2017\[a\]](#); [Hall, 2017\[b\]](#); [Majji, 2016](#); [Li, 2013](#); [Pradeep, 2010](#); [Pradeep, 2012](#); [Salian, 2010](#); [Sufi, 2016 \[a\]](#); [Sufi, 2016 \[b\]](#); [Young, 2016](#); [Zang, 2016](#)) and two 24-week clinical studies ([Hall, 2017\[b\]](#); [Mason, 2017](#)) support the long-

Property of Haleon- Confidential

May not be used, divulged, published or otherwise disclosed without the consent of Haleon

term anti-sensitivity efficacy of 5% w/w CSPS-containing toothpastes, with twice daily use. The aim of the current 8-week study is to confirm the clinical efficacy of a 5% CSPS toothpaste. Changes to the formulation, compared to those previously investigated, include removal of the opacifier, addition of a blue pigment, introduction of a new flavor for improved in-use experience, and modification of the dental abrasive system for improved stain removal and enamel polishing benefits. None of these changes are expected to impact the occlusion mode of action (MoA) of CSPS and the anti-sensitivity efficacy of a 5% CSPS toothpaste.

In addition to confirming the longer-term DH efficacy of the investigational 5% CSPS toothpaste, time to onset of DH relief will be investigated, with clinical assessments completed after 3-, 7-, 14- and 28-days twice-daily use. At all assessment time points (3-, 7-, 14-, 28- and 56-days), the efficacy of the 5% CSPS toothpaste will be compared with that of a regular fluoride toothpaste with no known anti-sensitivity efficacy (negative control).

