4.6 Analysis of Other Variables

N/A.

5 Changes to the Protocol Defined Statistical Analysis Plan

There were no changes to the originally planned statistical analysis specified from the protocol version 2.0 (Dated: 06-Mar-2024).

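### The SAP omits two safety summaries that the protocol plans (hard-tissue changes by visit, and treatment-related serious AEs) while declaring no changes from the protocol

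*SAP*

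**What the plan says.** Protocol Section 12.3.4 sets out the safety outputs. Its AE displays are to be "AE summaries (number of distinct AEs and frequency/proportion of subjects affected) presented by treatment group and overall", and the last of them is "Treatment emergent treatment related serious AEs by SOC and PT". Below these it asks for listings, two of which carry a summary: soft-tissue (OST) findings with a summary of abnormalities by visit, and "OHT findings (with a summary of changes by visit").

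The SAP treats the two examinations differently. For soft tissue, Section 4.5.2.1 says "OST will be summarized (number of subjects and percentages with abnormalities, without abnormalities, or OST not examined) by visit and study product", and this becomes Table 14.3.4.1. For hard tissue, Section 4.5.2.2 ends with "OHT examination will be listed (Listing 16.2.8.2) for safety population" and plans nothing more. Section 14.3.4 of Appendix 1 holds one table, the OST one.

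For adverse events, SAP Section 4.5.1 plans four tables, 14.3.1.1 to 14.3.1.4. The one nearest to the protocol's serious-event summary is "Table of treatment related TEAEs by SOC and PT (Table 14.3.1.3"), which is not restricted to serious events. Serious events appear only in Listings 14.3.2.1 (deaths) and 14.3.2.2 (non-fatal SAEs).

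SAP Section 5 then states: "There were no changes to the originally planned statistical analysis specified from the protocol version 2.0".

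**The concern.** A SAP may drop or replace a planned output if it says so. Here two protocol-specified safety summaries disappear and the section reserved for declaring changes says there were none. If the SAP is followed as it stands, the study report will lack both outputs and may repeat an incorrect statement of conformity.

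The hard-tissue output is the more useful of the two. After treatment starts, OHT is the only examination that covers tooth surface loss, and it is scheduled once, at Day 56 (Protocol Section 8.2.6.5; the Day 3 procedures in Section 8.2.2.4, which Visits 4 to 6 repeat, list OST but not OHT). Protocol Section 2.1 also names, among the formulation changes, "modification of the dental abrasive system for improved stain removal and enamel polishing benefits". A reader of the report could reasonably look for a by-arm table of hard-tissue changes and would not find one. SAP Section 4.5 itself names OHT abnormalities among the things by which safety will be assessed.

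**Working it through.** **Reconciling the planned outputs**

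| Protocol 12.3.4 | SAP 4.5 and Appendix 1 | Result |
|---|---|---|
| TEAEs by SOC and PT | Table 14.3.1.1 | present |
| TEAEs by oral/non-oral and PT | Table 14.3.1.2 | present |
| Treatment-related TEAEs by oral/non-oral and PT | Table 14.3.1.4 | present |
| Treatment-related *serious* TEAEs by SOC and PT | Table 14.3.1.3 covers all treatment-related TEAEs; serious events are listed only | absent |
| OST findings with a by-visit summary | Table 14.3.4.1 and Listing 16.2.8.1 | present |
| OHT findings with a by-visit summary of changes | Listing 16.2.8.2 only | summary absent |

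The OHT change summary is planned once and appears zero times. The same holds for the related-serious table. Changes declared in SAP Section 5: zero.

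**Does a listing satisfy the OHT item?** The item sits under a heading for separate listings, so this has to be asked. The OST item directly above it has the same form under the same heading, and the SAP turned it into a table. On the SAP's own reading, the OHT item also calls for a summary.

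**Do the TEAE tables cover it?** Protocol Section 9.3.2 and SAP Section 4.5.2.2 make any new or worsened OHT observation an AE, so the events are counted by arm. Three things are lost:
- They are grouped by preferred term, not by OHT category.
- They are mixed with any other events coded to the same term.
- They are reported on the Safety population, which is everyone randomized and dosed (SAP Section 4.1.3), with no count of those examined at Day 56.

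**Size of the denominator gap**

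The inputs, from SAP Section 1.4, are 117 randomized and 105 completing per arm, with about 10% dropout.
- The plan's own figures reproduce: 105 / 0.90 = 116.7, rounded up to 117. A two-sample t-test with difference 0.25, SD 0.55 and 105 per arm has 90.6% power.
- Expected without a Day 56 OHT: 117 − 105 = 12 per arm.
- Ratio of a Safety-based rate to an examined-based rate: 105 / 117 = 0.897. For example, 10 affected subjects are 10/117 = 8.5% or 10/105 = 9.5%.
- With unequal dropout, assumed at 5% and 15%, a true rate of 10% in both arms would show as 9.5% and 8.5%, a ratio of 0.95 / 0.85 = 1.12.

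The 10 events, the 10% rate and the 5%/15% split are illustrations. The documents give none of them.

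**The case against.** The strongest reply is that no information is lost. Every OHT change becomes an AE and appears by arm in Tables 14.3.1.1 and 14.3.1.2 and, if classed as oral, in Listing 14.3.2.4. Listing 16.2.8.2 holds the subject-level findings, and Table 14.1.1 shows discontinuation by arm. For serious events, Table 14.3.1.3 is a superset of the missing table, and the SAE listings identify the individual cases. This stands: the gap is in the planned summaries, not in data capture. It does not explain why SAP Section 5 reports no changes.

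Four stronger readings are tempting and are not supported:

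- *A reader might infer that OHT is the only examination that looks for abrasion.* The Screening EAR examination (Protocol Section 9.1.1) does so too. OHT is the only such examination after treatment starts.
- *A reader might infer that the changed abrasive system is a known hard-tissue risk.* The protocol ties the change to stain removal and polishing and does not say that abrasivity rose. Section 2.2 describes the ingredients as having a history of safe use.
- *A reader might infer that uneven dropout could mask or create a difference between arms.* Equal dropout scales both arms alike and leaves their ratio unchanged. The 1.12 factor needs an assumed split and is small against the noise. With 10 and 9 events among 117 per arm, the risk ratio is 1.11; the SE of its log is √(1/10 − 1/117 + 1/9 − 1/117) = 0.44, so the 95% CI is about 0.47 to 2.6. These are descriptive outputs with no hypothesis test.
- *A reader might infer that the protocol requires subjects examined as the denominator.* It sets none. The SAP's OST table is for the Safety population with a not-examined category, so restoring the OHT summary on that model could also give Safety-based percentages. Showing the number examined is a recommendation.

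It is also too strong to say that subjects who leave early are never examined again. Protocol Sections 7.2 and 8.4 allow an oral examination at the investigator's discretion.

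**Conclusion.** The mismatch is certain. Two summaries planned in Protocol Section 12.3.4 are missing from the SAP text and from Appendix 1, and the statement in SAP Section 5 is therefore incorrect. The practical effect is modest: no planned display gives hard-tissue changes by OHT category and arm alongside the number examined. The 0.90 and 1.12 factors only indicate the order of magnitude. The first assumes that the planned 10% dropout equals the share without a Day 56 OHT; the second assumes a dropout split that the documents do not give.

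No consequence has been shown for the missing serious-event table beyond its absence. It may well be empty, since Protocol Section 2.2 calls adverse reactions to 5% CSPS toothpaste rare or very rare.

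The primary and secondary efficacy analyses, the sample size and the data collected are unaffected. This is a safety-reporting and consistency point that should be corrected before unblinding.

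**What to change.** 1. Add an OHT change table to SAP Section 4.5.2.2 and to Section 14.3.4 of Appendix 1 (for example as Table 14.3.4.2). By study product and visit, and for each OHT category, give the number examined, the number not examined (as in the OST table), and the number and percentage who went from absent to present or worsened relative to Screening. State the denominator. The worsened count matters: exposed dentin from erosion, abrasion or recession is an entry criterion, so some subjects may already have tooth surface loss recorded as present at Screening.
2. Add a table of treatment-related serious TEAEs by SOC and PT to SAP Section 4.5.1 and Appendix 1 Section 14.3.1. SAP Section 4.5.1 already provides for a null table if there is nothing to report.
3. Correct SAP Section 5. If either omission is intended, declare it there with the reason instead of adding the table.

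The cost is two table shells programmed from data already collected and one revised SAP statement. No change to study conduct is needed.
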